### 8.3 STATISTICAL ANALYSES

Data analysis will be conducted with condition masked. Descriptive analyses will be conducted first to examine the distributions of key variables and identify any unusual cases or outliers. Most outcome variables are expected to be normally distributed, but variables with substantially skewed distributions will be appropriately transformed so that linear models may be applied without violating assumptions.

Following inspection and interpretation of descriptive statistics, primary inferential data analyses will address the study's specific aims. Primary analyses will be conducted with the full sample using an intention-to-treat analytic approach.

The primary aim is to evaluate whether the website improves children's safety with firearms. This aim will be measured through scores from the quiz, photograph, and role play simulation tasks. We will standardize each outcome variable and evaluate through correlation matrices and factor analysis to determine if they appear to be measuring the same underlying construct. If so, they will be aggregated. Otherwise, they will be assessed as independent outcome variables.

Linear mixed models will evaluate our primary hypotheses. Linear mixed models were selected primarily because they offer the ability to allow for correlation within each child based on all three of the child's measurements. Group differences will be tested by fitting the following model:

$$E[Y_{ij} | X, Z] = \beta_0 + \beta_1 X_{\text{group}} + \beta_2 X_{\text{time}} + \beta_3 X_{\text{group}} * X_{\text{time}}$$

where time will be entered into the model as a categorical variable (baseline vs post vs follow-up) utilizing effect cell coding so that we can determine whether changes in the outcomes between different time points differ by intervention group. Of greatest interest will be  $\beta_3$ , as this parameter will tell us whether the effect of the intervention group differs between baseline, post-intervention and follow-up time points. If we find that  $\beta_3$  is significant, we will perform orthogonal contrasts to determine which specific time points differ from each other. To increase statistical efficiency, we will use previous literature to identify covariates that may be highly associated with the outcome before statistical analysis, and those covariates will be included in the linear model.

Secondary aims will evaluate efficacy of the ShootSafe program to improve relevant cognitive skills in two domains, impulse control and hypothetical thinking, and to improve children's perceptions of vulnerability, susceptibility and severity of injury, plus their perception of normative peer behavior. Analyses will follow using similar linear mixed models.

We anticipate missing data among the dataset for various reasons, including attrition from the study, rare participant refusal to conduct particular tests or answer particular questions and rare equipment failure or experimenter error. The planned linear mixed models allow the use of all observed data, including data from participants with incomplete missing outcome measurement at follow-up, with the relatively mild assumption of missing at random. We will handle missing covariate data through multiple imputation or other appropriate analytic strategies.

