#### 5.2 MEASURES TO MINIMIZE BIAS: RANDOMIZATION

Randomization to condition will be achieved using a 1:1 allocation ratio. The research team will determine randomized assignment through a random number generator and randomized order list concealed to all parties prior to assignment. Children will be assigned to a condition upon arrival to the first training visit, following all baseline data collection.

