### 8.2 SAMPLE SIZE DETERMINATION

A power analysis was conducted to determine sample size using PASS 14 (Power Analysis and Sample Size) software. Based on previous work, we conservatively assumed change of 3 (SD = 2) in the ShootSafe website condition and 2 (SD = 2) in the comparison condition, yielding an anticipated medium effect size of 0.5. That is, we powered to detect a difference of 0.5 standard deviations between the ShootSafe website and control condition groups. Using 2 tails and  $\alpha = .05$  and assuming an independent samples t-test is conducted, a sample size of 70 per group provides 90% power to detect an effect size as small as 0.5. With the same assumptions and retaining  $n = 70$  per group, we estimate 95% power to detect an effect size of at least 0.56. As we are using a linear mixed model to assess the specific aims rather than a t-test, we will ensure that power is higher yet than that determined above since we will incorporate the observed correlation between the trials. Conservatively inflating 15% to account for attrition, we propose a sample size of 162, which is amply large to test our hypotheses.

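### The primary mixed model leaves the baseline group difference free although baseline precedes randomization; a common-baseline model would cut contrast variance by (1−ρ)/2, and the promised power gain is not assured

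*Combined protocol and SAP*

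**What the plan says.** Section 5.2 fixes the order of events: "Children will be assigned to a condition upon arrival to the first training visit, following all baseline data collection". It also states "Randomization to condition will be achieved using a 1:1 allocation ratio".

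Section 8.3 gives the primary model. It has an intercept, a group term, a time term and their product, and "time will be entered into the model as a categorical variable (baseline vs post vs follow-up) utilizing effect cell coding". The interaction is the parameter of interest: "this parameter will tell us whether the effect of the intervention group differs between baseline, post-intervention and follow-up time points". If it is significant, contrasts between time points follow. Covariates are to be chosen from the literature to gain efficiency, and "those covariates will be included in the linear model". The form in which they enter is not given, and the baseline score is not named among them. On missing data the section says "The planned linear mixed models allow the use of all observed data, including data from participants with incomplete missing outcome measurement at follow-up".

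Section 8.2 bases the sample size on an independent-samples t-test of change (3 versus 2, SD 2, 70 per group, two-sided .05). It then says of the mixed model that "we will ensure that power is higher yet than that determined above since we will incorporate the observed correlation between the trials". It gives no correlation, covariance structure or mixed-model power.

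**The concern.** Group plus group-by-time over three visits gives three free group differences, one of them at baseline. Randomization after baseline makes that one zero in expectation. Estimating it anyway turns each later-versus-baseline component of the interaction into a plain difference in mean change. A change score subtracts the whole baseline value, when only the part that predicts the later score is useful.

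This is lost precision, not bias. Two statements in the plan also depend on it. Section 8.2 presents a power gain over the t-test as secured by the within-child correlation, and section 8.3 expects the covariates to add efficiency. If neither follows from the model as written, the trial has less margin than its authors believe.

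**Working it through.** **Inputs.** From section 8.2: difference in change 3 − 2 = 1, SD of change 2, n = 70 per arm, two-sided .05, total 162 (81 per arm), 15% attrition. From section 5.2: 1:1 allocation, baseline before assignment. Assumed: ρ, which the documents do not give, from .3 to .9; equal variances and compound symmetry unless stated. The SD of change is held at 2 throughout, so σ² = 4/[2(1−ρ)].

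**The plan's own figure.** The t-test variance is 2 × 4/70 = 0.1143. Noncentral t with 138 df gives 83.6% two-sided power, not the stated 90%; a one-sided test gives 90.3%. That is a separate discrepancy. The comparisons below start from 83.6%.

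**One later-versus-baseline contrast, complete data.**

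- Free baseline: 2σ²(1−ρ) × 2/n = 4 × 2/70 = 0.1143 at every ρ, the same as the t-test.
- Common baseline: σ²(1−ρ²) × 2/n.
- Ratio: (1−ρ²)/[2(1−ρ)] = (1+ρ)/2, a cut of (1−ρ)/2.

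| ρ | Common-baseline variance | Cut | Power | Equivalent n per arm, 70 ÷ (1+ρ)/2 |
|---|---|---|---|---|
| .3 | 0.0743 | 35% | 95.4% | 107.7 |
| .5 | 0.0857 | 25% | 92.4% | 93.3 |
| .7 | 0.0971 | 15% | 89.0% | 82.4 |
| .8 | 0.1029 | 10% | 87.2% | 77.8 |
| .9 | 0.1086 | 5% | 85.4% | 73.7 |

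A simulation of 20,000 trials at ρ = .5, with baseline as covariate standing in for the constrained model, gave a 25.7% cut and power of 83.6% versus 92.5%. The post-versus-follow-up contrast gains nothing.

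**The planned joint 2-df test.** Noncentrality is e′V⁻¹e, where e holds the two effects and V their covariance. Power is from the noncentral chi-square.

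- Sustained effect (1, 1): as written, (70/8)/0.75 = 11.67, power 87.4%. Constrained: 97.1, 93.8 and 91.8% at ρ of .5, .7 and .8.
- Effect halved at follow-up (1, 0.5): as written, 8.75, power 75.8%. The single contrast has the same noncentrality (1/0.1143 = 8.75), so the second degree of freedom is pure cost here. Constrained: 88.4, 83.1 and 80.5%.
- Decaying correlation (.5 adjacent, .25 baseline to follow-up), sustained effect: as written, 35 × 4/15 = 9.33, power 78.6%. Constrained: 35 × 3.75/9 = 14.58, power 93.8%.

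Using F with 137 denominator df lowers the three as-written figures to 86.6, 74.8 and 77.7%. The planned test can therefore lie above or below 83.6%.

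**Attrition.** With 81 per arm and 12 per arm (81 × .15 ≈ 12) lost after baseline, the post contrast goes from 84.4% to 92.0% at ρ = .5 and from 83.9% to 88.6% at ρ = .7.

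**Unequal variances.** The general ratio is Var(post)(1−ρ²)/Var(change). If the post SD is 1.3 times baseline, the cut is 9% (ρ = .5) or 1% (ρ = .7). If it is 0.8 times, the cut is 43% or 37%.

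**Covariates.** Take a child-level covariate explaining 25% of the variance at each visit, with ρ = .5 and σ² = 4. The residual variance is 3 and the residual correlation (.5 − .25)/.75 = 1/3.

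- As written: the change variance is 2 × 3 × (1 − 1/3) = 4, so nothing is gained. In 600 simulated trials with 12 of 81 per arm lost after baseline, the variance ratio was .98.
- Constrained: 3 × (1 − 1/9) = 2.67, so the ratio falls from .75 to .667 and power reaches 94.9%. At ρ = .7 the ratio falls from .85 to .80 (90.7%).

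**The case against.** The planned analysis is conventional, valid and answers the question section 8.3 asks. A sharper estimator is an optimization, not the repair of an error. That is right, and the point claims no more for the model; the sentence in section 8.2 is the only statement that is unsupported.

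The size of the gain rests on values the documents do not give. ρ is unknown, section 8.3 expects that some variables may be skewed and transformed, and the endpoint may be one composite or three scores, each with its own ρ. This stands: the gain must be read as a range, and it is close to nothing if variance grows and ρ is high.

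Nor is the ratio's bound of 1 exact in practice. It holds for a known covariance. With an estimated baseline slope and 40,000 simulated trials at 70 per arm, variance rose 0.6% at an SD ratio of 1.43 with ρ = .7, and 0.8% at a ratio of 2 with ρ = .5. These losses are trivial beside the likely gains.

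The mixed model can beat the t-test: under compound symmetry with a sustained effect it does (86.6 to 87.4% against 83.6%). So the correct statement is that higher power is not assured, not that it is false. Section 10 says other aspects are in the published and IRB protocols, so covariate form or covariance structure might be given there. The combined document should still state them.

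**Conclusion.** The concern holds as an improvement in precision that needs no new data. Baseline is complete before assignment, the primary model ignores this, and under equal variances and complete data a common baseline mean cuts the variance of each later-versus-baseline contrast by (1−ρ)/2. Over the assumed ρ of .3 to .9 that is 35% down to 5%. The cut is larger if variance falls after baseline and may nearly vanish if it rises.

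The power claim in section 8.2 has no support as written. Its SD belongs to the change, so the t-test already contains the baseline-to-post correlation. The joint test can fall below the t-test under plausible effect and correlation patterns. Covariates entered as child-level main effects do not rescue precision in this model. The change should be made, though the trial's conclusions would be valid without it.

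**What to change.** **Section 8.3.** Fit a constrained longitudinal mixed model. Make baseline the reference time level, with one common baseline mean and no group term at baseline. Estimate group effects at post and follow-up, test them jointly on 2 df and then report each visit. Use an unstructured within-child covariance. Keep intention-to-treat and all observed data. Name the prognostic covariates, state the form in which they enter, and put them in this model. Entering baseline as a covariate gives the same gain when baselines are complete. Because the plan expects some missing data, the constrained model fits it better.

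**Section 8.2.** Replace the sentence on higher power. Say that mixed-model power depends on the effect at follow-up and on the within-child correlation. Add that a common baseline mean reduces the variance of each later-versus-baseline contrast by (1−ρ)/2 under equal variances, and state the assumed ρ.

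**Cost.** A revised model statement, which also replaces the effect coding, the reading of β₃ and the follow-on contrasts, and carries to the secondary models; plus two sentences of text. No new data, visits or children are needed. The constraint holds in expectation because assignment follows baseline collection.

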## 9 SUPPORTING DOCUMENTATION AND OPERATIONAL CONSIDERATIONS

### 9.1 REGULATORY, ETHICAL, AND STUDY OVERSIGHT CONSIDERATIONS

#### 9.1.1 INFORMED CONSENT PROCESS

##### 9.1.1.1 CONSENT/ASSENT AND OTHER INFORMATIONAL DOCUMENTS PROVIDED TO PARTICIPANTS

Consent forms describing in detail the study intervention, study procedures, and risks are given to the participants' parents and written documentation of informed consent is required prior to conducting study screening procedures. Verbal assent will be obtained from child participants.

#### 9.1.1.2 CONSENT PROCEDURES AND DOCUMENTATION

Informed consent is a process that is initiated prior to the individual's agreeing to participate in the study and continues throughout the individual's study participation. Consent forms will be Institutional Review Board (IRB)-approved and the participant's parent or legal guardian will be asked to read and review the document. The investigator will explain the research study and answer any questions that may arise. A verbal explanation will be provided in terms suited to both the participant's and the child's comprehension of the purposes, procedures, and potential risks of the study and of their rights as research participants. Participants will have the opportunity to carefully review the written consent form and ask questions prior to signing. The participant will sign the informed consent document prior to engaging in any study procedures. Participants will be informed that participation is voluntary and that they may withdraw from the study at any time, without prejudice. The informed consent process will be conducted and documented in the source document (including the date), and the form signed.

#### 9.1.2 STUDY DISCONTINUATION AND CLOSURE

This study may be temporarily suspended or prematurely terminated if there is sufficient reasonable cause. Written notification, documenting the reason for study suspension or termination, will be provided by the suspending or terminating party to regulatory authorities. If the study is prematurely terminated or suspended, the Principal Investigator (PI) will promptly inform study participants and the Institutional Review Board (IRB), will provide the reason(s) for the termination or suspension. Study participants will be contacted, as applicable, and be informed of changes to study visit schedule.

Circumstances that may warrant termination or suspension include, but are not limited to:

- Determination of unexpected, significant, or unacceptable risk to participants
- Demonstration of efficacy that would warrant stopping
- Insufficient compliance to protocol requirements
- Data that are not sufficiently complete and/or evaluable
- Determination of futility

The study may resume once concerns about safety, protocol compliance, and data quality are addressed, and satisfy the IRB.

#### 9.1.3 CONFIDENTIALITY AND PRIVACY

Participant confidentiality and privacy is strictly held in trust by the participating investigators and their staff. Therefore, study documentation, data, and all other confidential information generated will be held in strict confidence. No information concerning data will be released to any unauthorized third party without prior written approval of the Principal Investigator.

Representatives of the Institutional Review Board (IRB) may inspect all documents and records required to be maintained by the investigator.

The study participant's contact information will be securely stored for internal use during the study. At the end of the study, all records will continue to be kept in a secure location for as long a period as dictated by the reviewing IRB and/or Institutional policies.

Study participant research data, which is used for purposes of statistical analysis and scientific reporting, will be stored securely. Individual participant research data will be identified by a unique study identification number.

---

#### 9.1.4 DATA HANDLING AND RECORD KEEPING

---

##### 9.1.4.1 DATA COLLECTION AND MANAGEMENT RESPONSIBILITIES

Data collection is the responsibility of the research team under the supervision of the Lab Manager, Study Biostatistician, and Principal Investigator. The Principal Investigator is responsible for ensuring the accuracy, completeness, legibility, and timeliness of the data reported.

---

##### 9.1.4.2 STUDY RECORDS RETENTION

Study documents will be retained for a minimum of 3 years after the completion of the study or longer if required by local regulations.

---

#### 9.1.5 PROTOCOL DEVIATIONS

A protocol deviation is any noncompliance with the clinical trial protocol requirements. The noncompliance may be either on the part of the participant, the investigator, or the study site staff. As a result of deviations, corrective actions will be developed and implemented.

These practices are consistent with ICH GCP:

- 4.5 Compliance with Protocol, sections 4.5.1, 4.5.2, and 4.5.3
- 5.1 Quality Assurance and Quality Control, section 5.1.1
- 5.20 Noncompliance, sections 5.20.1, and 5.20.2.

It is the responsibility of the Principal Investigator to use continuous vigilance to identify and report deviations within 10 working days of identification of the protocol deviation. Protocol deviations must be sent to the reviewing Institutional Review Board (IRB) per their policies. The Principal Investigator is responsible for knowing and adhering to the reviewing IRB requirements.

## 9.2 ABBREVIATIONS

|         |   |
|---------|---|
| AE      | Adverse Event                                       |
| ANCOVA  | Analysis of Covariance                              |
| CFR     | Code of Federal Regulations                         |
| CONSORT | Consolidated Standards of Reporting Trials          |
| CRF     | Case Report Form                                    |
| DHHS    | Department of Health and Human Services             |
| GCP     | Good Clinical Practice                              |
| HIPAA   | Health Insurance Portability and Accountability Act |
| ICH     | International Conference on Harmonisation           |
| ICMJE   | International Committee of Medical Journal Editors  |
| IRB     | Institutional Review Board                          |
| LSMEANS | Least-squares Means                                 |
| NCT     | National Clinical Trial                             |
| NIH     | National Institutes of Health                       |
| OHRP    | Office for Human Research Protections               |
| PI      | Principal Investigator                              |
| QA      | Quality Assurance                                   |
| QC      | Quality Control                                     |
| SAE     | Serious Adverse Event                               |
| SAP     | Statistical Analysis Plan                           |
| SOA     | Schedule of Activities                              |
| SOP     | Standard Operating Procedure                        |
| UP      | Unanticipated Problem                               |
| US      | United States                                       |

